**EXCLUSION CRITERIA:**

Subjects meeting any of the following criteria will be excluded from the study:

1. Subject is a female who is pregnant or breastfeeding or planning to become pregnant within 3 months after the last dose of study drug.
2. Subject has a history of any clinically significant conditions including:
  - Asthma treated with oral systemic steroids within the past 6 months
  - Diabetes mellitus (type 1 or 2), with the exception of gestational diabetes
  - Thyroidectomy or thyroid disease that required medication within the past 12 months
  - Serious angioedema episodes within the previous 3 years or requiring medication in the previous 2 years
  - Head trauma resulting in a diagnosis of traumatic brain injury other than concussion
  - Frequent episodes of headache.
3. Subject has received treatment in another clinical study of an investigational drug (or medical device) within 30 days or 5 half-lives (whichever is longer) before the first dose of study drug.
4. Subject has been previously enrolled in any clinical study involving TPOXX (tecovirimat).
5. Subject has a history of relevant drug and/or food allergies (ie, allergy to tecovirimat or excipients, or any significant food allergy that could preclude a standard diet in the study site).
6. Subject has any condition possibly affecting drug absorption (eg, previous surgery on the gastrointestinal tract, including removal of parts of the stomach, bowel, liver, gallbladder, or pancreas, with the exception of appendectomy).
7. Subject has evidence or history of clinically significant allergic (except for untreated, asymptomatic, seasonal allergies at time of the first dose of study drug), hematological, endocrine, pulmonary, gastrointestinal, cardiovascular, hepatic, psychiatric, or neurological disease. Exceptions to these criteria (eg, stable, mild joint disease unassociated with collagen vascular disease) may be made following discussions with the medical monitor.

8. Subject has a history of cardiac disease, symptomatic or asymptomatic arrhythmias, syncopal episodes, or risk factors for torsades de pointes (eg, heart failure, hypokalemia).
9. Subject has a family history of sudden cardiac death, not clearly due to acute myocardial infarction.
10. Subject has a seizure disorder or history of seizures (does not include childhood febrile seizures) or a past history that increases seizure risks such as significant head injury that caused loss of consciousness or other changes in the subject's daily function, concussion, stroke, central nervous system infection or disease, or alcohol or drug abuse or family history of idiopathic seizures.
11. Subject has a history of a peptic ulcer or significant gastrointestinal bleed.
12. Subject has a bleeding disorder diagnosed by a doctor (eg, factor deficiency, coagulopathy, or platelet disorder requiring special precautions) or significant bruising or bleeding difficulties with blood draws.
13. Subject has a malignancy that is active, or treated malignancy for which there is not reasonable assurance of sustained cure, or malignancy that is likely to recur during the period of the study (subject should be in complete remission for at least 5 years).
14. Subject has neutropenia or other blood dyscrasia determined to be clinically significant by the investigator.
15. Subject has used any of the following prohibited medications from within 7 days (or 5 half-lives, whichever is longer) before the first dose of study drug: antidiabetic medication; anticoagulants; anticonvulsants; substrates of the breast cancer resistance protein transporter including methotrexate, mitoxantrone, imatinib, irinotecan, lapatinib, rosuvastatin, sulfasalazine, and topotecan; substrates of CYP2C8 including repaglinide, paclitaxel, Montelukast, pioglitazone, rosiglitazone; and substrates of CYP2C19 including S-mephenytoin, clobazam, diazepam, rabeprazole, voriconazole, lansoprazole, and omeprazole. Medications not listed here that are known (or thought) to be CYP3A4 substrates may be allowed at the investigator's discretion, after consultation with the medical monitor, if administration poses little to no risk to the subject.
16. Subject has a history of drug or alcohol abuse or dependency within the last year before screening.
17. Subject has a history of an eating disorder.
18. Subject has a current or recent (<30 days before screening) history of clinically significant bacterial, fungal, or mycobacterial infection.
19. Subject has a current clinically significant viral infection.
20. Subject has a known clinically significant chronic viral infection (eg, human T cell lymphotropic virus I or II).
21. Subject has consumed grapefruit or grapefruit juice, Seville orange or Seville orange-containing products (eg, marmalade), or caffeine- or xanthine-containing products within 48 hours before the first dose of study drug or throughout the study.
22. Subject has used any prescription (excluding hormonal birth control) or over-the-counter medication (including herbal or nutritional supplements) within 14 days before the first dose of study drug.

23. Subject demonstrates long-term use ( $\geq 14$  consecutive days) of glucocorticoids including oral or parenteral prednisone or equivalent ( $>20$  mg total dose per day) or high-dose inhaled steroids ( $>800$  mcg/day of beclomethasone dipropionate or equivalent) within the preceding 1 month (low-dose [ $\leq 800$  mcg/day of beclomethasone dipropionate or equivalent] inhaled and topical steroids are allowed).
24. Subject has donated  $>450$  mL blood or blood components within 30 days before the first dose of study drug. The investigator should instruct subjects who participate in this study to not donate blood or blood components for 4 weeks after the completion of the study.
25. Subject is a smoker or has used nicotine or nicotine-containing products (eg, cigarettes, electronic vapor cigarettes, cigars, chewing tobacco, snuff, nicotine patches, or nicotine gum) within 6 months before the first dose of study drug.
26. Subject has consumed pomegranate or pomegranate juice, pomelo fruits or pomelo juice, or alcohol within 72 hours before the first dose of study drug.
27. Subject reports participation in strenuous activity or contact sports within 24 hours before the first dose of study drug.
28. Subject has known hepatitis B or C infection or positive test for hepatitis B surface antigen, hepatitis C virus antibody, or human immunodeficiency virus type 1 or 2 antibodies at screening.
29. Subject has a positive test result for amphetamines (including methamphetamines and ecstasy/methylenedioxymethamphetamine), barbiturates, benzodiazepines, cannabinoids (including tetrahydrocannabinol), cocaine metabolites, opiates (including heroin, codeine, and oxycodone), or alcohol at screening or check-in.
30. Subject has any of the following laboratory test results within 28 days before the first dose of study drug:
  - Estimated serum creatinine clearance (Cockcroft-Gault)  $<90$  mL/min
  - Creatinine in males  $>1.7$  mg/dL and in females  $>1.4$  mg/dL (1.3 times the upper central laboratory reference range)
  - Hemoglobin  $\leq 10\%$  of the lower central laboratory reference range
  - White blood cell count not within the central laboratory reference range
  - Absolute neutrophil count  $<1000$  cells/mm^3
  - Platelets not within  $\pm 10\%$  of central laboratory reference range
  - Alanine aminotransferase  $>1.5$  times above the upper central laboratory reference range
  - Aspartate aminotransferase  $>1.5$  times above the upper central laboratory reference range
  - Alkaline phosphatase  $>20\%$  above the upper central laboratory reference range
  - Hemoglobin A1c  $\geq 7.0\%$
  - Cholesterol  $\geq 300$  mg/dL and low-density lipoprotein  $\geq 190$  mg/dL.
31. Subject has a blood pressure considered to be clinically significant by the investigator. Blood pressure may be retested twice in the sitting position at 5-minute intervals.

32. Subject has a resting heart rate of <40 beats per minute or >100 beats per minute at screening.
33. Subject has an abnormal ECG at screening that is determined by the investigator to be clinically significant.
34. Male subject has a QTcF >450 ms or female subject has a QTcF >470 ms at screening or Day -1.
35. In the opinion of the investigator, the subject is not suitable for entry into the study.

#### **EVALUATION PROCEDURES:**

##### **Pharmacokinetic Assessments:**

Blood samples for PK analysis of TPOXX will be collected from all subjects on Day 1 before study drug administration (0 hour), at 0.5, 1, 2, 4, 6, 8, 12 (before the PM dose), 14, 16, 18, 20, and 24 hours (before the AM dose on Day 2), on Day 6 (before the AM dose and 4 hours after the AM dose), on Day 7 before the AM dose (0 hour), at 0.5, 1, 2, 4, 6, 8, 12 (before the PM dose), 14, 16, 18, 20, and 24 hours (Day 8, 24 hours after the AM dose on Day 7), and on Day 9 (48 hours after the AM dose on Day 7).

For PK samples, the acceptable window for collection from the scheduled collection time point will be as follows:  $\pm 5$  minutes for the time points from 1 to 8 hours and  $\pm 15$  minutes for the 12- to 48-hour time points.

The following plasma PK parameters will be calculated for TPOXX using actual sampling times rather than scheduled sampling times and will include but are not limited to:

- Area under the plasma concentration-time curve (AUC) from time 0 to the last quantifiable measurement ( $AUC_{0-t}$ )
- AUC from time 0 extrapolated to infinity ( $AUC_{0-\infty}$ )
- AUC from time 0 to 24 hours ( $AUC_{0-24}$ )
- AUC during the first dosing interval ( $\tau = 12$  hours) ( $AUC_{0-\tau}$ )
- Maximum drug concentration in plasma ( $C_{max}$ )
- Time to  $C_{max}$  ( $T_{max}$ )
- Apparent volume of distribution ( $V_d/F$ )
- Apparent total body clearance ( $CL/F$ )
- Concentration observed prior to the next dose administration ( $C_{trough}$ )
- Terminal elimination half-life ( $t_{1/2}$ )
- Terminal elimination rate constant ( $\lambda_z$ )
- Percentage of  $AUC_{0-\infty}$  extrapolated from the last quantifiable measurement to infinity ( $\%AUC_{extrap}$ ).

**Safety Assessments:**

Safety and tolerability will be assessed by monitoring and recording of AEs, clinical laboratory test results (hematology, serum chemistry, pregnancy, and urinalysis), vital sign measurements (systolic and diastolic blood pressures, heart rate, respiratory rate, and body temperature), 12-lead ECG results, and physical examination findings.

**STUDY DRUG, DOSAGE, AND ROUTE OF ADMINISTRATION:**

TPOXX, 600 mg (3 × 200-mg capsules), will be administered orally twice daily, approximately 12 hours (±30 minutes) apart, on Days 1 through 7.

**STATISTICAL METHODS:**

Complete, detailed statistical methods will be described in the statistical analysis plan.

**Sample Size:**

The sample size (N = 36 [to allow at least 32 enrolled subjects to complete]) for this study is based on clinical and practical considerations and not on a formal statistical power calculation. The sample size is considered sufficient to effectively assess the PK and safety profiles of TPOXX.

**Analysis Populations:**

- The Safety Population will include all subjects who receive at least 1 dose of study drug.
- The PK Population will include subjects who receive study drug and have sufficient concentration data to facilitate the calculation of PK variables.

**Pharmacokinetic Analyses:**

Individual plasma concentration and time deviation data will be presented in a data listing. Plasma concentration data will be listed and summarized using the following descriptive statistics: number of subjects, arithmetic mean, standard deviation (SD), coefficient of variation (CV), geometric mean, geometric CV, median, minimum, and maximum. Individual and mean plasma concentration versus time profiles will be presented in figures on both linear and semilogarithmic scales.

The PK parameters of TPOXX will be analyzed based on the actual sampling times. All parameters will be determined using noncompartmental methods using Phoenix® WinNonlin® Version 8.0 or higher (Certara, L.P., Princeton, New Jersey) or SAS® Version 9.4 or higher (SAS Institute Inc., Cary, North Carolina).

The individual PK parameters and weight-normalized PK parameters will be presented in data listings and summarized using the following descriptive statistics: number of subjects, arithmetic mean, SD, CV, median, minimum, maximum, geometric mean, geometric SD, and geometric CV.

**Safety Analyses:**

Adverse events will be coded by preferred term and system organ class using the latest version of the Medical Dictionary for Regulatory Activities and summarized overall. All AE data will be presented in a data listing. Treatment-emergent AEs will be summarized overall, as well as by severity and relationship to study drug. Serious AEs and AEs leading to

discontinuation of study drug will also be presented in the data listings and summarized overall.

Actual values and changes from baseline for clinical laboratory test results, vital sign measurements, and 12-lead ECG results will be summarized at each time point using descriptive statistics (number of subjects, mean, SD, median, minimum, and maximum). Shift tables will be generated for clinical laboratory test results. Clinical laboratory data, vital sign measurements, 12-lead ECG results, and physical examination findings will be presented in data listings.

**DATE OF PROTOCOL:** 02 August 2019

## **1. INTRODUCTION**

### **1.1 BACKGROUND**

Historically, variola virus (VARV), the etiologic agent of smallpox, has been one of the more important human pathogens. Smallpox is highly communicable and carries exceptionally high morbidity. Secondary attack rates from 30% to 80% have been reported among unvaccinated members of households. Mortality rates range from 1% for variola minor to 30% for variola major. With the advent of biowarfare as an instrument of terrorism, smallpox can no longer be thought of as a disease only of historic impact.

In July 2018, the FDA approved the oral formulation of TPOXX for the treatment of patients with human smallpox disease caused by VARV.

### **1.2 RATIONALE FOR STUDY**

This study is being conducted as an FDA post marketing commitment to the approved New Drug Application for TPOXX. SIGA is required to conduct a study to determine the pharmacokinetic (PK) profile of TPOXX in subjects with a body weight greater than 120 kilograms (>120 kg) to determine if a change in dosing regimen would be needed in these patients.

### **1.3 POTENTIAL RISKS AND BENEFITS**

#### **1.3.1 Potential Risks**

The effect of TPOXX on a fetus or nursing baby is not yet known; therefore, women of childbearing potential participating in this study will be required to agree to use an acceptable means of birth control from 30 days before the first dose of study drug and continuing through 30 days after the last dose of study drug. Pregnancy testing will be performed at the screening visit and checked by the investigator for negative pregnancy before administration of study drug on Day -1. Women who are pregnant or lactating or plan to become pregnant within 3 months after study drug administration will be excluded from the study; if a female subject becomes pregnant during study participation, study drug dosing will be discontinued, and the subject will be withdrawn from the study (Section 6.2.1.9).

As with all drugs, there is potential risk of an allergic reaction. At this time, there is no definitive information on the allergic activity of TPOXX. Headache and nausea have been the most common AEs in clinical studies completed to date. There may be other side effects

of TPOXX that are not yet known. Full details can be found in the TPOXX full prescribing information.

### **1.3.2 Known Potential Benefits**

As this study will be conducted in subjects free from smallpox, no direct health benefits from taking the study drug are expected. Study subjects may benefit from receiving the laboratory testing, ECGs, and physical examinations. Others may benefit from knowledge gained in this study that may aid in the development of a drug for the treatment of smallpox.

## **2. STUDY OBJECTIVES**

### **2.1 PRIMARY OBJECTIVE**

The primary objective of this study is to determine the PK profile of 600 mg oral TPOXX (3 × 200-mg capsules) administered twice daily (BID) for 7 days in adult subjects weighing more than 120 kg to determine if a change in dosing regimen would be needed in these patients.

### **2.2 SECONDARY OBJECTIVE**

The secondary objective of this study is to evaluate the safety and tolerability of 600 mg oral TPOXX administered BID for 7 days in adult subjects weighing more than 120 kg.

## **3. STUDY POPULATION**

Approximately 36 male and female subjects will be enrolled at a single center in the United States to achieve at least 32 evaluable enrolled subjects.

### **3.1 INCLUSION CRITERIA**

Each subject must meet all the following criteria to be enrolled in this study:

1. Subject is male or female between 18 and 50 years of age, inclusive.
2. Subject has a body weight >120 kg at screening, at check-in on Day -1, and prior to dosing on Day 1.
3. Women of childbearing potential, have a negative  $\beta$  human chorionic gonadotropin pregnancy test (serum) at the screening visit and a confirmatory negative serum

- pregnancy test on Day –1 before receipt of study drug, and meet 1 of the following criteria:
- a. The subject or their partner has undergone surgical sterilization
  - b. The subject is postmenopausal, defined as 12 consecutive months with no menses without an alternative medical cause and has a documented plasma follicle-stimulating hormone level  $>40$  IU/mL
  - c. The subject agrees to be abstinent (ie, heterosexually inactive or women in a religious order)
  - d. The subject agrees to consistently use 1 of the following methods of contraception from the beginning of screening (which they had been consistently using for at least 30 days before the first dose of study drug) through 30 days after the last dose of study drug:
    - i. Condoms, male or female, with a spermicide  
**NOTE:** For male subjects, condoms must be used for 90 days after the last dose of study drug.
    - ii. Diaphragm or cervical cap with spermicide
    - iii. Intrauterine device with spermicide
    - iv. Oral contraceptives or other hormonal methods  
**NOTE:** Subject must agree to use an additional nonhormonal method of contraception in conjunction with oral contraceptives.
    - v. Male sexual partner who had undergone a vasectomy at least 3 months before screening.
  4. Male subjects must agree to not donate sperm from the first dose of study drug through 90 days after the last dose of study drug.
  5. Subject is considered by the investigator to be in good general health as determined by medical history (no hospitalizations for chronic medical conditions in the previous 2 years), clinical laboratory results, vital sign measurements, 12-lead ECG results, and physical examination findings at screening.
  6. Subject agrees to comply with all protocol requirements.
  7. Subject is able to provide written informed consent.
  8. Subject agrees to comply with the dietary requirements.

9. Subject does not intend to lose weight (diet or weight loss) from the screening visit and throughout the study.

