### **3.3 OTHER SCREENING CONSIDERATIONS**

#### **3.3.1 Subject Restrictions During the Study**

- Subjects must be willing to remain confined at the study site from check-in (Day –1) until safety assessments are completed on Day 9.
- Subjects who have abnormal physical examination findings or an ongoing AE/SAE on Day 9 that is deemed related to study drug or per investigator or SIGA discretion will return to the study site on Day 14 (+2 days) for a follow-up visit.

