#### **6.2.1.9 Reporting of Pregnancy**

Pregnant women are not eligible to participate in the study. Subjects must be counseled regarding prevention of pregnancy and encouraged to make every effort to avoid pregnancy during study participation. If a female subject becomes pregnant during study participation, study drug dosing will be discontinued, and the subject will be withdrawn from the study. The pregnancy itself is not considered an SAE. However, the investigator must complete the pregnancy report form and fax it to PPD Pharmacovigilance within 24 hours of knowledge of the pregnancy. After delivery or termination of pregnancy, the follow-up pregnancy report form should be completed and submitted via fax to PPD Pharmacovigilance. Spontaneous abortions should always be reported as SAEs. Pregnancy data will be captured and followed by PPD. All pregnancies and outcomes will be tracked. The case will not be closed until after the child is followed for 3 months.

If there are complications during the pregnancy, the complications will be recorded as AEs in the usual manner. The subject will be asked to report the outcome of the pregnancy. If there is a congenital anomaly in the infant, this will be recorded as an SAE in the data forms for the mother (ie, the study subject).

If a subject becomes pregnant during the study after receiving the study drug, all safety evaluations will be collected as per protocol. In addition, at the time that the pregnancy is reported, consent will be requested to contact the subject and her physician in the postpartum period to assess delivery and health status of the neonate.

If the partner of a male subject becomes pregnant, the partner will be asked for consent to allow her treating physician to provide SIGA or its designee with follow-up information regarding the pregnancy and its outcome.

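### Inclusion criterion 3a accepts a partner's sterilisation of any age, so the 3-month wait after vasectomy in 3d(v) never decides eligibility

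*Protocol*

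**What the plan says.** Criterion 3 in Section 3.1 applies to women of childbearing potential. It requires negative serum pregnancy tests at screening and on Day -1, "and meet 1 of the following criteria". The lettered options are therefore alternatives. Two of them bear on a sterilised partner:

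- 3a: "The subject or their partner has undergone surgical sterilization". No interval is given.
- 3d(v): "Male sexual partner who had undergone a vasectomy at least 3 months before screening". This is one of the methods under 3d, whose opening text also requires consistent use for at least 30 days before the first dose. That text governs 3d only.

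The synopsis carries the same two options. Section 1.3.1 gives the reason for the contraception requirement, "The effect of TPOXX on a fetus or nursing baby is not yet known", and sets its span for women of childbearing potential as follows: "use an acceptable means of birth control from 30 days before the first dose of study drug and continuing through 30 days after" dosing ends. Inclusion criterion 6 adds a general undertaking: "Subject agrees to comply with all protocol requirements".

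**The concern.** Option 3d(v) shows that the authors consider a vasectomy done less than 3 months before screening too recent to rely on. Option 3a, one of its alternatives, accepts the same vasectomy unconditionally. A safeguard that can always be bypassed through another option is not a safeguard, and the investigator is left with two rules that give opposite answers on the same fact.

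What is at stake is possible fetal exposure, not the pharmacokinetic analysis. A woman relying solely on a partner's recent vasectomy can be enrolled and then discharged on Day 9, with 28 days of the required contraception window still to run. This is eligibility wording, which belongs in the protocol and would not be settled in a statistical analysis plan.

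**Working it through.** The plan gives no figure to reproduce. The check is one of logic, followed by day counts.

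**Logic.** Criterion 3 is met if a OR b OR c OR d. Assume that a vasectomy counts as surgical sterilisation of the partner.

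- Any woman who meets 3d(v) has a partner with a vasectomy, so she already meets 3a.
- Any woman whose partner had a vasectomy less than 3 months before screening fails 3d(v) but meets 3a.

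Enumeration confirms this. Eight vasectomy states (none, or 0.5, 1, 2, 2.9, 3, 6 or 24 months before screening) were crossed with yes/no for own sterilisation, 3b, 3c and any of 3d(i) to (iv): 8 × 2 × 2 × 2 × 2 = 128 combinations.

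- Deleting the 3-month wait from 3d(v) changes 0 of 128 decisions.
- Adding the same wait to the partner part of 3a changes 4 of 128, all from eligible to ineligible: vasectomy at 0.5, 1, 2 or 2.9 months with no other qualifying route.

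**Day counts.** Inputs from Section 4: screening on Day -28 to Day -2, discharge on Day 9, last dose on Day 7, Day 37 falling 30 days after the last dose. There is no Day 0. Three months is taken as 90 days (an assumption).

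Elapsed days: Day -28 to Day 1 = 28; Day -2 to Day 1 = 2; Day 1 to Day 9 = 8; Day 1 to Day 37 = 36; Day 9 to Day 37 = 28.

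*Reading 1: 3a taken literally, with the vasectomy on the day of screening as an example.*

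| Screened | Age at Day 1 | Age at Day 9 | Age at Day 37 | Short of 90 at Day 37 |
|---|---|---|---|---|
| Day -28 | 28 | 28 + 8 = 36 | 28 + 36 = 64 | 90 - 64 = 26 |
| Day -2 | 2 | 2 + 8 = 10 | 2 + 36 = 38 | 90 - 38 = 52 |

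*Reading 2: Section 1.3.1, through criterion 6, limits 3a to a vasectomy at least 30 days old at Day 1.*

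- The most recent one allowed is 30 days old at Day 1, 30 + 8 = 38 at Day 9 and 30 + 36 = 66 at Day 37, so 90 - 66 = 24 days short.
- Age at Day 1 below which the whole post-discharge period lies inside 90 days: 90 - 36 = 54.
- Age at Day 1 from which none of it does: 90 - 8 = 82.
- So all 28 days are inside for ages 30 to 53, some for 54 to 81, and none from 82. The last boundary can move by one day depending on whether the discharge day is counted.

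*What 3d(v) would require at Day 1.* Screened Day -2: 90 + 2 = 92 days. Screened Day -28: 90 + 28 = 118 days. Even under Reading 2, therefore, 3a admits vasectomies aged 30 to 91 days (screened Day -2) or 30 to 117 days (screened Day -28) at Day 1 that 3d(v) would reject.

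**The case against.** The strongest reply is that a specific rule should control a general one. Only 3d(v) names vasectomy, so 3a should be read as leaving vasectomy to it. That is a sensible guess at intent, but the text does not say it. The options are expressly alternatives, and 3a names the partner; with vasectomy taken out, little is left for that word to cover. The enumeration does not settle this point, because it builds in the assumption that 3a includes vasectomy. It shows only what follows from the wording once that is granted.

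A second reply is that the acceptable birth control called for in Section 1.3.1 must mean what 3d(v) accepts, so the 3 months come in that way. But 3a is itself one of the listed routes, so the word does not select 3d(v) over 3a. What Section 1.3.1 does state is a 30-day lead-in before dosing, which is Reading 2.

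A third reply is that the 90-day yardstick at Day 37 is not in the protocol, since 3d(v) measures its interval at screening, and that no harm is shown. This is fair. The day counts describe how recent the vasectomy could be. They are not a risk estimate.

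Other protections also stand. Both serum pregnancy tests apply, and "Subjects must be willing to remain confined at the study site from check-in" until Day 9, so the dosing days are covered. "Subjects must be counseled regarding prevention of pregnancy and encouraged to make every effort to avoid pregnancy" during participation. Exclusion 1 removes women planning pregnancy, and exclusion 35 leaves room for investigator judgement. None of these sets an interval after vasectomy, but together they keep the residual risk small.

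**Conclusion.** The point holds on the wording as it stands: the 3-month condition in 3d(v) cannot change an eligibility decision, in Section 3.1 or in the synopsis. It rests on one assumption, that a vasectomy is surgical sterilisation of the partner, and on the absence of any text giving 3d(v) priority over 3a.

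Its weight is low. It affects only a woman of childbearing potential whose sole qualifying route is a partner's vasectomy under 3 months before screening, in a study of about 36 men and women. The protocol gives no frequency for this and none is estimated. The objectives, sample size and analysis are untouched. It is worth correcting because the protocol's own pregnancy safeguard does not operate within its own contraception window, and the correction is cheap.

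**What to change.** Either limit 3a to the subject's own surgical sterilisation and leave partner vasectomy to 3d(v), or add the condition of at least 3 months before screening to the partner part of 3a. Make the same edit in Section 3.1 and the synopsis.

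The cost is one line in two places, with no added procedures or subjects. The few women affected would need another 3d method, already in use for 30 days before the first dose, or would have to qualify by abstinence under 3c.

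As a purely clerical matter, the same amendment could correct Sections 3.4.1, 5.3.1 and 5.3.1.2, which refer to Sections 4.1 and 4.2 (5.3.1.2 to 4.2 only), although the eligibility criteria are in 3.1 and 3.2. That slip adds nothing to the weight of this point.
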